### 2.2.3 Other Outcomes

- Changes in fundus photographs,
- Changes in serum antibodies or IFN-γ ELISPOT responses to AAV,

• Number and proportion of participants with rAAV2tYF-CB-hRS1 vector DNA detectable in blood by PCR assay

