### 4.2 Subject Exclusion Criteria

All subjects meeting any of the following exclusion criteria prior to enrollment will be excluded from study participation:

- 1. Prior receipt of any AAV gene therapy product,
- 2. Any of the following mutations in the RS1 gene: R141H, C59S or C223S,
- 3. Serum anti-AAV neutralizing antibody titer against AAV2tYF >1:20,
- 4. Pre-existing eye conditions that would contribute significantly to visual loss or increase the risk of an intravitreal injection (e.g. advanced glaucoma, uveitis or large retinal detachment),
- 5. Lens, cornea, or other media opacities that preclude adequate visualization and testing of the retina,
- 6. Use of anticoagulants or anti-platelet agents within 7 days prior to study agent administration,
- 7. Use of any investigational agent within 3 months prior to enrollment,
- 8. Any condition which leads the investigator to believe that the participant cannot comply with the protocol requirements or that may place the participant at an unacceptable risk for participation.

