3.3 Other Outcome Variables

Other outcome variables include the following:

- Change over time in fundus photographs,
- Change over time in titers of serum antibodies or IFN-γ ELISPOT responses to retinoschisin (RS1).
- Change over time in serum antibodies and IFN-γ ELISPOT responses to AAV, and
- The number and proportion of participants with rAAV2tYF-CB-hRS1 vector DNA detectable in blood by polymerase chain reaction (PCR) assay.

4. Study Design and Procedures

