14.7 Indirect Ophthalmoscopy

An indirect ophthalmoscopy examination of the vitreous, disc, macula, vessels, lens, and periphery will be performed at each visit. Shifts from baseline to worst value during follow-up will be tabulated.

Subject listings of indirect ophthalmoscopy results will also be produced.

15. Efficacy Analyses

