15.9 Fundus Photography

Fundus photography will be performed at the baseline visit and at the visit 12 months after study agent administration.

The results will be summarized using counts and percentages for each group and for all subjects at each visit for each eye. Percentages will be based on the number of subjects with responses. Fundus

08 August 2017

photography parameters include Any evidence of increased inflammation, Hemorrhage, Retinal detachment, Is there RPE disturbance or atrophy in the fovea, Any changes from baseline visit. A subject listing of the fundus photograph parameters will also be produced.

16. Long-term Follow-Up (LTFU)

After the completion of 9 study visits over the course of one year after study agent administration, longterm follow-up (LTFU) will be conducted annually for an additional 4 years after the Month 12 visit. In accordance with regulatory guidance for gene therapy clinical trials, information will be obtained about any cancer, neurological, autoimmune or hematological disorder that developed or worsened since the last visit. A subject listing containing this information will be provided.

17. Interim Analysis

No interim analysis will be conducted for this study. Preliminary analyses of available data may be conducted during the study.

18. Data and Safety Monitoring Committee

Refer to section 4.1.

19. Changes from Protocol-Stated Analyses

- Change over time in titers of serum antibodies and IFN-γ ELISPOT responses to retinoschisin (RS1) is moved from secondary safety outcomes to other outcomes.
- Inferential statistics for all efficacy endpoints will be calculated.
- Visual field parameter (square root of the loss variance) will not be read by the Reading Center.

20. References

¹ Hood DC and Birch DB. A computational model of the amplitude and implicit time of the b-wave of the human ERG. Vis Neurosci 1992;8:107-26

² Patel PJ, Chen FK, Da Cruz L, Rubin GS, and Tufail A. *Test-retest variability of reading performance metrics using MNREAD in patients with age-related macular degeneration*. Invest Ophthalmol Vis Sci 2011;52:3854-9

21. Revision History

Documentation of revision to the SAP will commence after approval of the Final version 1.0.

22. Tables

Table Number	Title
Table 14.1.1	Subject Disposition
Table 14.1.2	Demographics

Table 14.1.3	Vital Signs
Table 14.1.4	Medical History
Table 14.1.5	Concomitant Medications
Table 14.2.1.1	Best Corrected Visual Acuity

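### The fundus-photograph table gives counts by visit, not change within the eye, so new findings are not summarized although change is the stated outcome

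*SAP*

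**What the plan says.** Both documents define the outcome as change. The SAP (3.3 Other Outcome Variables) has "Change over time in fundus photographs" and the protocol (2.2.3 Other Outcomes) has "Changes in fundus photographs". In each it sits below the primary and secondary outcomes.

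On timing, SAP 15.9 states: "Fundus photography will be performed at the baseline visit and at the visit 12 months after study agent administration". The visit schedule adds a photograph at early termination.

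On analysis, 15.9 states: "The results will be summarized using counts and percentages for each group and for all subjects at each visit for each eye". It continues: "Percentages will be based on the number of subjects with responses". Five items are named:

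- three record presence: hemorrhage, retinal detachment, and disturbance or atrophy of the retinal pigment epithelium (RPE) in the fovea;
- one asks about increased inflammation;
- one is "Any changes from baseline visit".

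The list of tables has one entry for fundus photography, Table 14.2.9, and no shift table. Section 15.9 also plans a subject listing (Listing 16.2.6.11), and SAP 9.4 says listings run by group, subject and visit.

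The SAP treats comparable data differently. For indirect ophthalmoscopy (14.7) it says: "Shifts from baseline to worst value during follow-up will be tabulated". Section 14.5 does the same for the slit lamp, and 14.2.1 plans shifts from baseline for hematology and chemistry.

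**The concern.** A percentage at baseline and a percentage at Month 12 are two margins of a two-by-two table. The outcome, change within an eye, lies in the cells. An eye in which a finding clears offsets an eye in which it appears, and the margins can stay level or fall while new lesions occur. Because the denominator is whoever has a response at that visit, the two percentages may not even describe the same eyes.

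The distinction matters in this disease. Protocol 1.2.1 describes the XLRS retina as fragile and liable to vitreous hemorrhage and detachment. Protocol 1.3.1 lists detachment among the risks of the agent, and hemorrhage and detachment among the risks of the injection. The same finding can therefore be long-standing disease or a new harm, and safety is the primary objective.

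The change item does not fill the gap. It does not say which finding changed or whether the eye got better or worse. That item and the increased-inflammation item also compare with an earlier state, so they have no natural reading at baseline, yet the text summarizes every item at each visit.

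**Working it through.** The plan gives no figure for this point, so there is nothing to reproduce. The check asks how much the planned table reveals about new findings. All counts and rates below are assumed for illustration. Group sizes are the plan's: 3 in each of Groups 1A, 1B, 2 and 3, up to 6 in 2A, up to 15 in 4, and about 27 participants in all.

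**Step 1. Bounds from the two margins.** Among *n* eyes photographed at both visits, let *a* be positive at baseline and *b* at Month 12. New findings lie between max(0, *b* − *a*) and min(*b*, *n* − *a*).

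| n | a | b | New findings |
|---|---|---|---|
| 3 | 1 | 1 | 0 to 1 |
| 6 | 2 | 2 | 0 to 2 |
| 15 | 3 | 3 | 0 to 3 |
| 27 | 3 | 3 | 0 to 3 |
| 27 | 5 | 7 | 2 to 7 |
| 27 | 10 | 10 | 0 to 10 |
| 27 | 0 | 2 | exactly 2 |

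The last row is the important exception: if no eye has the finding at baseline, the planned counts give the number of new cases exactly.

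**Step 2. Does the change item settle it?** Take 27 eyes, hemorrhage 3 at both visits, detachment 2 at both, and 4 eyes marked as changed. With equal margins, each new case is matched by one resolved case, so *k* new hemorrhages require 2*k* changed eyes. Since 2*k* ≤ 4, *k* can be 0, 1 or 2. The same holds for detachment, and the same eyes may change on both. Every combination of 0 to 2 new hemorrhages with 0 to 2 new detachments fits. The item narrows the range for hemorrhage but does not fix it.

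**Step 3. Size of the discrepancy.** Suppose half of the baseline findings resolve and 10% of unaffected eyes develop one. With baseline prevalence *p*, Month 12 prevalence is 0.5*p* + 0.10(1 − *p*), and new findings are 0.10(1 − *p*).

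| p | Month 12 prevalence | Net change | New findings |
|---|---|---|---|
| 0% | 10% | +10 points | 10% |
| 5% | 2.5 + 9.5 = 12% | +7 | 9.5% |
| 10% | 5 + 9 = 14% | +4 | 9% |
| 20% | 10 + 8 = 18% | −2 | 8% |
| 30% | 15 + 7 = 22% | −8 | 7% |

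The net change understates new findings by the share that resolved, 0.5*p*. It is nil when no eye is affected at baseline and grows with baseline prevalence.

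**Step 4. How often would offsetting occur within a group?** At *p* = 20%, an eye resolves with probability 0.20 × 0.5 = 0.10 and has a new finding with probability 0.80 × 0.10 = 0.08. With independent eyes, the chance of at least one of each is 1 − 0.90^n − 0.92^n + 0.82^n:

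- n = 3: 1 − 0.7290 − 0.7787 + 0.5514 = 0.04
- n = 6: 1 − 0.5314 − 0.6064 + 0.3040 = 0.17
- n = 15: 1 − 0.2059 − 0.2863 + 0.0510 = 0.56
- n = 27: 1 − 0.0581 − 0.1053 + 0.0047 = 0.84

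On these rates, offsetting is rare in the smallest groups and likely only in a full Group 4 and in the all-subjects column.

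**The case against.** The strongest reply is that no information is lost. With about 27 subjects and two scheduled photographs each, anyone can pair the visits in Listing 16.2.6.11 and count new findings. This stands. A reader might infer from 15.9 that new lesions cannot be told from old ones at all; the listing planned in that same section rules that out.

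The second reply is that harm is captured elsewhere. Protocol 7.2 makes slit lamp, tonometry and indirect ophthalmoscopy the principal means of detecting ocular adverse events, the SAP tabulates shifts for two of these, and treatment-emergent events are summarized by eye. This stands in part. Ophthalmoscopy shifts are by structure (vitreous, disc, macula, vessels, lens, periphery) and do not name the three photographic findings. The protocol's adverse-event definition (7.2.1.1) takes in conditions first detected after administration even if they were there before, so the event tables do not cleanly separate new from old.

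The third reply is that baseline hemorrhage or detachment may be uncommon. A reader might take "advanced glaucoma, uveitis or large retinal detachment" in exclusion criterion 4 to mean that only a large detachment bars entry. The text does not support that: these are examples, and the criterion covers any pre-existing eye condition that would contribute significantly to visual loss or raise the injection risk. If baseline findings are rare, the planned counts come close to the number of new ones. The documents do not say how rare they are.

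Lastly, it is tempting to argue that the small groups make cancellation easy. Step 4 shows the opposite.

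**Conclusion.** The point holds in a limited form. Table 14.2.9 does not summarize the outcome that both documents name, because it shows margins where within-eye change is wanted and its one change item lacks direction. The gap exists only for findings that some eyes already have at baseline, and its size is the number that resolve. The documents give no baseline frequencies, so the rates in steps 3 and 4 are illustrative only.

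The impact is low. This is a descriptive outcome in the lowest tier, 15.9 plans no test on it, the listing keeps the full information, and other safety tables overlap with it. It is a free improvement to one table, not a defect in the safety assessment.

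A reader might go further and ask for the change item to be split into better, worse and mixed. The documents do not show that direction was recorded, so that could need the photographs to be graded again. It should not be asked for unless direction is already in the data.

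**What to change.** Revise the shell of Table 14.2.9:

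- For hemorrhage, retinal detachment and foveal RPE disturbance or atrophy, cross-tabulate baseline (absent, present) against Month 12 (absent, present) within the eye.
- Restrict each cross-tabulation to eyes with a reading at both visits, and state how many eyes lack one.
- Show study eye and fellow eye separately, by group and overall, in line with the shift tables of SAP 14.5 and 14.7.
- Show the increased-inflammation and any-change items at Month 12 only.
- Keep Listing 16.2.6.11 as planned.

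The cost is one table shell and its program, with no new data and no new reading of photographs. SAP section 1 allows additional analyses if the study report identifies them, so the table can be added there without reopening anything else.
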